**Figure 2. Effects of subcutaneous injections of r-hIL-7 on gut mucosal T-cells at week 12 in people with HIV**

*PLoS Pathogens*, Volume 10, Issue 1, Jan 2014.  
<https://journals.plos.org/plospathogens/article?id=10.1371/journal.ppat.1003890>

HIV viremia (“blips”) that were of unclear significance. This was followed by a phase II study of IL-7 in patients with HIV observed HIV RNA blips >50 copies/mL, occasionally exceeding 200 copies/mL, which prompted delay of subsequent IL-7 doses ([Thiebaut et al. 2016](#)). The clinical relevance of these viral “blips” is unclear; it is possible that it represents expansion of T cells but not replication-competent HIV. Experience to date suggests “blips” are short lived, lasting less than 4 weeks in ACTG5214.

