### 2.4.1 Risk Benefit Analysis in HIV associated Kaposi Sarcoma

Cancer is the leading cause of death in people with HIV. KS is associated with 40% mortality in HIV clinics in the US and Canada. Scalable T cell modulating therapies with minimal toxicities are highly desirable for KS. Based on the literature to date, the benefits of an effective immunotherapy for KS outweigh the theoretical risk of increasing the HIV reservoir. We hypothesize that NT-I7 will have a favorable therapeutic index in people with KS. Optimizing the dosing schedule will be important in the evaluation of NT-I7 in this patient population. CD4 lymphocytopenia in people living with HIV has a specific etiology and is substantially unique from other cancer populations. KS responses based on changes in CD4 counts have been established in the setting of HIV, distinguishing it from other cancers. The dosing schedule for this proposal is based on PD data from short acting IL-7 in people living with HIV and no cancer (Figure 1). In this study by Thiébaut *et. al.*, participants received weekly IL-7 for 3 weeks, had a peak CD4 count on week 4 that gradually declined over time. The CD4 count at week 4 decreased from peak but remained elevated compared to baseline. NT-I7 (IL-7-Fc) has much longer serum half-life than IL-7. The proposed schedule was suggested by NeoImmuneTech (NIT). NIT has preclinical data showing that over stimulation from too frequent dosing might have a negative effect. At present there does not appear to be a compelling rationale for more frequent dosing in HIV associated cases. This Phase I study will evaluate the kinetics of peripheral and tumor T cell expansion after the first and second doses of NT-I7. Evaluation of the safety of NT-I7 will include stopping rules for clinically significant events related to treatment of HIV (i.e., induction of HIV viremia with a drug resistant strain; clinical AIDS-defining events attributed to HIV viremia and associated immune decline despite demonstration of HIV adherence) as well as detailed evaluation of the effects on the HIV reservoir.

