## 6.4 Duration of Therapy

In the absence of treatment delays due to adverse event(s), treatment may continue for *up to 27 weeks (4 cycles/doses)* or until one of the following criteria for discontinuation of therapy applies:

- Disease progression requiring systemic therapy
- Intercurrent illness that prevents further administration of treatment

- Unacceptable adverse event(s)
- Dose limiting toxicity
- Participant decides to withdraw from the study
- General or specific changes in the patient's condition render the patient unacceptable for further treatment in the judgment of the investigator
- Participant not adhering to study schedule and procedures
- Dosing interruption lasting >12 weeks
- Pregnancy
  - All women of child bearing potential should be instructed to contact the investigator immediately if they suspect they might be pregnant (e.g., missed or late menstrual period) at any time during study participation.
  - The investigator must immediately notify CITN in the event of a confirmed pregnancy in a patient participating in the study.
- Termination of the study by sponsor
- The drug manufacturer can no longer provide the study agent

The reason(s) for protocol therapy discontinuation, the reason(s) for study removal, and the corresponding dates must be documented in the Case Report Form (CRF).

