### **Dose modifications for Adverse Events:**

Adverse Events from NT-I7 are expected to be mild and infrequent, as well as transient and Grade 2 or less (as noted in the AE list, [Section 10](#)). If a patient experiences a clinically significant and/or unacceptable toxicity, dosing should be interrupted, or the dose should be reduced per guidelines below and supportive therapy administered per standard clinical practice.

A maximum of two dose reductions will be allowed for an individual patient. If the second dose reduction is not tolerated, study treatment should be permanently discontinued, and the patient should be followed for safety per protocol guidelines.

NT-I7 administration will be held if the ALC is greater than 10,000 cells/ $\mu$ L. A blood draw will be performed prior to dosing on Day 1 of each cycle. Elevated ALC levels which have not resolved to  $\leq$  Grade 1 and/or requiring more than a 72-hour delay in administration of NT-I7 must be discussed with the Study Sponsor. Grade 3 lymphocyte count increase ( $>20,000$  cells/ $\mu$ L) is a normal physiologic response to the study treatment.

Below are dose management tables for the following AEs: fatigue, nausea, vomiting, diarrhea, neutropenia, thrombocytopenia, and hepatic damage.

Event Name	Fatigue
Grade of Event	Management/Next Dose for NT-I7
$\leq$ Grade 1	No change in dosing schedule
Grade 2	No change in dosing schedule
Grade 3	Hold* until $\leq$ Grade 2
Grade 4	Off protocol therapy

\*Patients requiring a delay of  $>72$  hours should go off protocol therapy.

Recommended management: physician discretion

Event Name	Nausea
Grade of Event	Management/Next Dose for NT-I7
$\leq$ Grade 1	No change in dosing schedule
Grade 2	No change in dosing schedule
Grade 3	Off protocol therapy if with adequate/maximal medical intervention symptoms persist
Grade 4	Off protocol therapy

Patients requiring a delay of  $>72$  hours should go off protocol therapy.

Recommended management: antiemetics

Event Name	Vomiting
Grade of Event	Management/Next Dose for NT-I7
≤ Grade 1	No change in dosing schedule
Grade 2	No change in dosing schedule
Grade 3	Off protocol therapy if with adequate/maximal medical intervention symptoms persist
Grade 4	Off protocol therapy
Patients requiring a delay of >72 hours should go off protocol therapy.	
Recommended management: antiemetics	

Event Name	Diarrhea
Grade of Event	Management/Next Dose for NT-I7

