≤ Grade 1	No change in dosing schedule
Grade 2	No change in dosing schedule
Grade 3	Off protocol therapy if with adequate/maximal medical intervention symptoms persist
Grade 4	Off protocol therapy
Patients requiring a delay of >72 hours should go off protocol therapy.	
Recommended management: physician discretion	

Event Name	Neutropenia
Grade of Event	Management/Next Dose for NT-I7
≤ Grade 1	No change in dosing schedule
Grade 2	No change in dosing schedule
Grade 3	Hold* until ≤ Grade 2
Grade 4	Off protocol therapy
*Patients requiring a delay of >72 hours should go off protocol therapy.	
Recommended management: treatment of infection as appropriate	

Event Name	Thrombocytopenia
Grade of Event	Management/Next Dose for NT-I7
≤ Grade 1	No change in dosing schedule
Grade 2	No change in dosing schedule
Grade 3	Off protocol therapy
Grade 4	Off protocol therapy
Patients requiring a delay of >72 hours should go off protocol therapy.	
Recommended management: platelet transfusion if indicated	

Event Name	Hepatic Damage
Grade of Event	Management/Next Dose for NT-I7
≤ Grade 1	No change in dosing schedule
Grade 2	No change in dosing schedule 
Grade 3	Off protocol therapy
Grade 4	Off protocol therapy
Patients requiring a delay of >72 hours should go off protocol therapy.	
Recommended management: physician discretion	

Event Name	HIV Viremia
Grade of Event	Management/Next Dose for NT-I7
HIV RNA > lower limit of detection and 400 copies /mL	No change in dosing schedule. Monitor HIV viral load 4 weeks later.
HIV RNA >400-1000 copies/mL	Repeat measurement in 4 weeks. Hold next cycle until plasma HIV RNA < 400 copies/mL. Evaluate adherence to medication.
HIV RNA >1000 copies/mL	Repeat measurement in 4 weeks. Hold next cycle until plasma HIV RNA < 400 copies/mL. If repeat > 1000 copies/mL, evaluation for HIV drug resistance
DLT (Section 6.2.1.)	Off protocol therapy
Patients requiring a delay of >72 hours should go off protocol therapy.	
Recommended management: physician discretion	

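### The HIV stopping rules announced in Section 2.4.1 do not work as written: no action follows a resistance result, the AIDS-event item needs 90 days inside a 28-day window, and a dose withheld for viremia falls under two conflicting rules

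*Combined protocol and SAP*

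**What the plan says.** Section 2.4.1 commits the safety evaluation to "stopping rules for clinically significant events related to treatment of HIV (i.e., induction of HIV viremia with a drug resistant strain", and then names AIDS-defining clinical events attributed to viremia in adherent patients. The places that should carry this out are as follows.

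- **Section 7, HIV viremia table.** Values up to 400 copies/mL leave dosing unchanged. Above 400, HIV RNA is repeated in 4 weeks and the instruction is "Hold next cycle until plasma HIV RNA < 400 copies/mL". Above 1000, the table adds "If repeat > 1000 copies/mL, evaluation for HIV drug resistance". The last row takes a participant off therapy for a DLT under Section 6.2.1. The footer reads "Patients requiring a delay of >72 hours should go off protocol therapy".
- **Section 7, introduction to the tables.** It names "fatigue, nausea, vomiting, diarrhea, neutropenia, thrombocytopenia, and hepatic damage". HIV viremia is not in the list, although its table follows with the same footer as the other seven.
- **Section 6.4.** Grounds for stopping include "Dosing interruption lasting >12 weeks", a DLT, an unacceptable adverse event and investigator judgment. Resistance is not mentioned there, in Section 6.2.1 or in Section 9.
- **Sections 6.2 and 6.2.1.** A DLT must occur in the first 28 days. The HIV-specific item, placed under criterion 5 (Grade 3 or 4 laboratory values), is an AIDS-defining opportunistic infection with a new, persistent HIV RNA above 400 copies/mL over 90 days despite adherence.
- **Section 3.1.5.** HIV-positive participants enter with HIV RNA of 40 copies/mL or less.

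**The concern.** Section 2.4.1 uses these rules to support its judgment that benefit outweighs the HIV risk, so they should be usable at a site. Three gaps appear when the sections are read together.

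1. A positive resistance result changes nothing in the table that orders the test.
2. The table's route off therapy leads to an item whose time requirement exceeds the window in which a DLT can occur.
3. When a due dose is withheld for viremia, one site can hold and later resume while another removes the participant permanently, and both can cite the same table.

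At stake is the consistent handling of a safety event that the protocol itself singles out. No efficacy estimate or dose-escalation decision is shown to change.

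**Working it through.** The plan gives no figure to reproduce, so the check compares time windows.

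**Inputs.** Doses at weeks 0, 9, 18 and 27; HIV RNA at screening, weeks 0, 4, 9, 13, 18, 27 and end of treatment at week 36 (Section 11). Repeat interval 4 weeks = 28 days; footer 72 hours = 3 days (Section 7). Interruption limit 12 weeks = 84 days (Section 6.4). DLT window 28 days (Section 6.2). AIDS-event persistence 90 days (Section 6.2.1). Assumption: after a value above 400, no repeat is done sooner than the 4 weeks the table prescribes, unless the calendar already schedules one.

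**Resistance.** The evaluation is triggered by a repeat above 1000. The hold ends when HIV RNA falls below 400. Neither step refers to the resistance result, and no DLT or discontinuation criterion does either. Only the general grounds in Section 6.4 remain.

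**AIDS event.** Shortfall against the 28-day window: 90 − 28 = 62 days. Sections 9.1.1.1 and 11 also describe the window as Week 0 Day 1 through Week 4 Day 7, which counted literally is 5 × 7 = 35 days; then 90 − 35 = 55 days. Adding the full 28 days of screening to the 28-day window gives 28 + 28 = 56 days, still below 90, and entry at 40 copies/mL or less means the elevation must start later than that. Later confirmation does not help, because Section 6.2.1 has the cohort assessed once the 28-day window is complete.

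**Hold against footer.**

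- *Value above 400 at week 9, 18 or 27, known before dosing, with the hold applied to that dose.* The repeat falls at week 13, 22 or 31, so the delay is 28 days. If the sample was drawn 72 hours early (Section 11, footnote k), 28 − 3 = 25 days; beyond the +2-day visit window, 25 − 2 = 23 days. The footer allows 3.
- *Value above 400 at week 4 or 13.* The repeat falls at week 8 or 17, 7 days before the dose. If it is below 400, no dose is delayed and there is no conflict. If it is not, the calendar sample at the dosing visit could still release the hold. If that also fails, the next 4-weekly repeat is at week 12 or 21, which is 3 × 7 = 21 days after the due date (21 − 4 = 17 allowing 2 days at each end).
- *Value at week 9 or 18 known only after dosing.* Repeats fall at +4 and +8 weeks and the next dose at +9. The conflict arises only if clearance has not occurred by then; the next repeat, at +12 weeks, is again 21 days late. After week 27 there is no further dose.

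The 12-week limit has room for 84 ÷ 28 = 3 repeats. The 72-hour footer has room for none.

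**The case against.** The strongest reply is that the AIDS-event stop exists. The table's last row cites Section 6.2.1, the list of criteria, rather than Section 6.2, where the window is set. The HIV item in that list closely tracks Section 2.4.1, and Section 6.5 speaks of DLTs during later treatment. This shows intent and stands as such: a reader might infer that the protocol contains no AIDS-event stop, and that would be wrong. But Section 6.2 defines every DLT by the 28-day window, so the intended rule cannot operate. A related Grade 3 or higher infection can be a DLT under item 1, but only inside that window.

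A reader might also infer that a participant with proven resistance will be re-dosed. The documents do not support that. Evaluation follows only a repeat above 1000, when the hold already applies. The footer then removes anyone whose due dose slips more than 72 hours, and Section 6.4 gives general grounds to stop. As written, re-dosing needs a fall below 400 before the dose is due, which is a narrow route.

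Nor do the hold and the footer conflict in every episode, as a quick reading might suggest: viremia found at week 4 or 13 that clears at the repeat causes none. Because the calendar places week 9 in Cycle 2, the next cycle after a week-9 result could even be read as Cycle 3, in which case the 28-day delay at week 9 does not arise.

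Finally, removal could be preferred to a hold, and it is the more cautious choice. The background gives the hold only weak support. Earlier blips were "occasionally exceeding 200 copies/mL, which prompted delay of subsequent IL-7 doses" and "are short lived, lasting less than 4 weeks", but values up to 400 fall in the no-change row, and those data come from short-acting IL-7, whereas Section 2.4.1 says NT-I7 has a much longer half-life. That objection stands: hold or removal is the sponsor's decision. What cannot stand is having both.

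**Conclusion.** The point holds in three limited parts. No action is tied to a positive resistance result. The HIV-specific DLT item cannot be met within the DLT window, falling short by 62 days (55 on the literal week count). The hold rows and the footer conflict when a due dose is actually withheld, with a delay of 21 to 28 days on the nominal schedule against 3. The last part assumes no repeat sooner than 4 weeks other than the calendar samples; an earlier test showing less than 400 could avoid it.

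The number of participants affected is not given and is probably small, since entry requires suppressed HIV RNA and the background describes earlier blips as brief. This should be corrected because a stated safety rule cannot be met and two stated rules disagree, not because a trial result is threatened.

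A minor related point: Section 2.4.1 also promises a detailed evaluation of effects on the HIV reservoir, but no reservoir assay, objective or analysis is planned. The viral load listed among the correlative assays in Table 7 is KSHV.

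**What to change.** (a) Add to the viremia table and to Section 6.4: *Confirmed new HIV drug resistance with viremia: off protocol therapy.*

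(b) Move the AIDS-event item out of the 28-day DLT list into Section 6.4 as a discontinuation criterion for the whole treatment period, and point the table's off-therapy row to it. Keep its definition (above 400 copies/mL over 90 days despite adherence) unless the sponsor justifies another.

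(c) State one rule for viremia. The table's rows and the 12-week limit favour the hold, with the 72-hour footer deleted from this table only. If the hold is kept, (a) must be adopted with it; otherwise a participant with proven resistance who falls below 400 within 12 weeks could resume dosing. If the sponsor prefers removal, delete the hold wording instead.

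Minor: in Section 2.4.1, replace the reservoir promise with a statement that plasma HIV RNA will be followed at the calendar visits.

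Cost: wording changes in Sections 2.4.1, 6.2.1, 6.4 and 7, with no new visit or assay. A few participants may stop earlier for resistance, and a hold is less cautious than removal.

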## 2.5 Correlative Studies Background

[figure not shown]
### 2.5.1 Pre-clinical Studies

In pre-clinical studies, NT-I7 has demonstrated potent anti-tumor efficacy, both as a monotherapy and in combination with chemo/radiotherapy and immune checkpoint inhibitors (CPIs). By increasing peripheral and tumor infiltrating lymphocytes, and increasing T cell functionality, NT-I7 synergizes with therapies such as chemotherapy, radiation, and CPIs. In a thymectomy-induced lymphopenia model (TILP) of C57BL/6MC-38-bearing mice, a combination of NT-I7 and anti-PD had significant anti-tumor effects that exceeded those of NT-I7 or anti-PD-1 therapies alone. The combination treatment increased intratumoral CD4+ and CD8+ T cell infiltration compared to treatment with either agent alone (Figure 4).

**Figure 4: Synergistic anti-tumor efficacy of NT-I7 and anti-PD-1 combination therapy is associated with a greater increase in CD4+ and CD8+ T cell infiltration than in monotherapy.**

NT-I7 and anti-PD-1 combination therapy is further associated with a less exhausted phenotype of CD8+ TILs, where surface expression of co-inhibitory receptors PD-1 and TIM-3 was reduced CD8+ TILs (Figure 5). A positive correlation between the number of CD8+ TILs and the suppression of tumor growth suggests that the combo therapy of NT-I7 with anti-PD-1 might increase tumor-specific cytotoxic CD8+ T cells.

**Figure 5: NT-I7 monotherapy promotes an immune-favorable tumor microenvironment (TME).**

A separate experiment evaluating 10mg/kg NT-I7 as a monotherapy in an MC-38 tumor model demonstrated that administration of NT-I7 created an immune-favorable tumor microenvironment (TME) by increasing the amount of tumor-infiltrating lymphocytes (TIL), the ratio of CD8+ Ts to regulatory Ts and MDSCs in the TME, and increasing the proliferative and effector capacity of CD8+ TIL.

### 3. PATIENT SELECTION

#### 3.1 Eligibility Criteria

- 3.1.1 Patients must have histologically confirmed Kaposi sarcoma.
- 3.1.2 Patients must have evaluable disease.  
Note: Kaposi sarcoma will be evaluated using a modified version (consistent with NCI studies) of the AIDS Clinical Trial Group (ACTG) Oncology Committee staging and response definitions for KS.
- 3.1.3 No upper or lower limit on the number of prior therapies or stage of disease. No prior systemic therapy (other than ART for HIV) or local therapy is required.
- 3.1.4 HIV-positive patients must have been on effective anti-retroviral (ART) therapy for at least 3 months prior to enrollment, with persistent KS affecting quality of life due to

either T1 disease or T0 disease with inadequate disease regression on ART alone.

3.1.5 HIV-positive patients must have undetectable HIV viral loads  $\leq$ 40 copies/mL measured using an FDA-approved commercial assay with lower limit of detection between  $\leq$ 20 copies/mL and  $\leq$  40 copies/mL.

3.1.6 Patients with visceral involvement must:

- Meet other eligibility criteria
- Have any/all associated tumor associated symptoms  $\leq$  Grade 2 by CTCAE criteria; and/or
- Require no immediate intervention (e.g., mild oozing of oral KS not an exclusion criteria)

3.1.7 Patients must provide newly obtained core, punch, or excisional biopsy of a tumor lesion obtained up to 28 days prior to treatment initiation. An archival tumor sample obtained within 1 year of screening is allowed if pre-treatment biopsy is deemed unsafe or technically not feasible.

3.1.8 Patients must be  $\geq$ 18 years of age on day of signing informed consent document. Because no dosing or adverse event data are currently available on the use of NT-I7 in patients  $<$ 18 years of age, children are excluded from this study but will be eligible for future pediatric trials.

3.1.9 ECOG performance status  $\leq$ 2 (Karnofsky  $\geq$ 60%, see [Appendix A](#)).

3.1.10 Patients must have adequate organ and marrow function as defined below:

- leukocytes	$\geq$ 2,500/mcL
- absolute neutrophil count	$\geq$ 1,000/mcL
- platelets	$\geq$ 100,000/mcL
- hemoglobin	$\geq$ 9/dL
- total bilirubin	$\leq$ 1.5 institutional upper limit of normal (ULN) OR $<3 \times$ institutional ULN for Gilbert's syndrome or HIV protease inhibitors
- AST(SGOT)/ALT(SGPT)	$\leq$ 2.5 $\times$ institutional ULN
- creatinine	$\leq$ 2 $\times$ institutional ULN OR
- creatinine clearance	$\geq$ 60 mL/min/1.73 m  by Cockcroft-Gault:  $\frac{(140 - \text{age}) \times (\text{weight in kg}) \times (0.85 \text{ if female})}{72 \times (\text{serum creatinine in mg/dL})}$

At the discretion of the treating physician, a 24-hour urine creatinine clearance could be obtained and utilized as the gold standard if creatinine clearance by Cockcroft-Gault is  $<$ 30 and prevents patient enrollment on the trial.

- 3.1.11 Patients with chronic hepatitis B virus (HBV) infection must be on suppressive antiviral therapy.
- 3.1.12 Patients with a history of hepatitis C virus (HCV) infection must have an undetectable HCV viral load due to prior treatment or natural resolution.
- 3.1.13 Female patients of childbearing potential must have a negative urine or serum pregnancy test within 72 hours before receiving the first dose of the study agent. If the urine test is positive or cannot be confirmed as negative, a serum pregnancy test will be required.
- 3.1.14 The effects of NT-I7 on the developing human fetus are unknown. For this reason and because NT-I7 may have an adverse effect on pregnancy and poses risk to the human fetus, women of child-bearing potential and men must agree to use adequate contraception (hormonal or barrier method of birth control; abstinence) prior to study entry, for the duration of study participation, and for 90 days after the last dose of study treatment. Should a woman become pregnant or suspect she is pregnant while she or her partner is participating in this study, she should inform her treating physician immediately. Men treated or enrolled on this protocol must also agree to use adequate contraception prior to the study, for the duration of study participation, and for 90 days after completion of NT-I7 administration.
- 3.1.15 Ability to understand and the willingness to sign a written informed consent document.
- 3.1.16 Patients with impaired decision-making capacity will not be excluded.

